### **9.1.1. Missing and Partial AE Onset Dates**

Rules for handling missing or partial AE Onset Dates are included in Section [5.6.2](#).

### **9.1.2. Summaries of Adverse Events**

TEAEs and OTAEs are summarized by treatment based on year of AE onset and overall. For each treatment, SOC, and PT, the number and percentage of patients reporting an event is calculated. In summary tables, SOC is presented alphabetically and events within each SOC are presented by decreasing frequency count.

Summary tables (number and percentage of patients and events) of TEAEs (by SOC and PT) are provided by treatment as follows:

- All TEAEs
- All related TEAEs (definitely, probably, or possibly related)
- All TEAEs by severity
- All serious TEAEs (including deaths)
- All non-serious TEAEs
- All related serious AEs (including deaths)
- All TEAEs leading to permanent discontinuation of study drug
- TEAEs by time to onset ( $\leq 12$  weeks and  $>12$  weeks)
- TEAEs exhibited in  $>5\%$  of patients

Listings are provided showing:

- All AEs
- Deaths
- Serious adverse events
- AEs leading to permanent discontinuation of study drug
- AEs leading to de-escalation of study drug

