#### **5.1.2.1. Fluid Overload**

Similar to endothelin receptor antagonists in certain patient populations, including bosentan in advanced congestive heart failure and avosentan in advanced CKD, bardoxolone methyl treatment was found to be associated with an increased risk for fluid overload and heart failure hospitalizations in the BEACON trial, which enrolled patients with Stage 4 CKD (eGFR 15 to 29 mL/min/1.73 m^2) and T2D. The overall increased risk for fluid overload and heart failure events with bardoxolone methyl appeared to be limited to up to four weeks after initiation of treatment. Elevated B-type natriuretic peptide (BNP) and prior hospitalization for heart failure were identified as risk factors that contributed to increased risk for these events. The increased risk for these events from bardoxolone methyl treatment had not been observed in six previous CKD studies, which were conducted mostly in patients with Stage 3b CKD (eGFR of 30 to 44 mL/min/1.73 m^2), patients with hepatic dysfunction, cancer patients, or healthy volunteers.

Review of admission notes and narrative descriptions for heart failure hospitalizations in BEACON indicates that heart failure in bardoxolone methyl-treated patients was often preceded by rapid fluid weight gain (several kilograms within the first weeks of treatment initiation) and was not associated with acute renal decompensation or acutely reduced left ventricular contractility. Available data from BEACON and other studies suggest that bardoxolone methyl treatment can differentially affect hemodynamic status according to the clinical condition of patients and likely promotes fluid retention in patients with more advanced renal dysfunction and other recognized risk factors associated with heart failure at baseline.

Risk mitigation procedures have been employed in subsequent trials to reduce the potential for bardoxolone methyl-induced fluid overload; these procedures excluded patients with the identified risk factors and ensured close monitoring for fluid retention within the first month of treatment.

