#### **5.1.2.2. Aminotransferase and Gamma-glutamyl Transferase Elevations**

In clinical studies of bardoxolone methyl, almost all patients had increases of aminotransferase enzymes above baseline upon initiation of treatment, which followed a consistent pattern. These increases were not associated with elevations in bilirubin or other signs of liver toxicity. In BEACON, fewer hepatobiliary serious adverse events (SAEs) were observed in the bardoxolone methyl arm than in the placebo arm. The elevations begin immediately after initiation of treatment or an increase in dose; they peak approximately two to four weeks later. In most patients, aminotransferase elevations were mild, but approximately 4% to 11% of patients experienced an elevation greater than 3X the upper limit of normal (ULN). The elevations resolved to levels less than the ULN in most all patients with elevations, within two weeks after peak values while patients continued taking study drug.

Patients who experienced elevations to greater than 3X the ULN sometimes required additional time to resolve. While some patients have had elevations to above 3X the ULN, persistent

elevations to above 3X the ULN have not been observed, and the elevations did not recur once resolved, unless caused by other factors.

Bardoxolone methyl regulates gamma-glutamyl transferase (GGT), a known Nrf2 target gene protein. In clinical studies, low level GGT elevations during treatment were common, mild, and typically lasted longer than alanine/aspartate aminotransferase (ALT/AST) elevations. Bilirubin levels in patients experiencing aminotransferase or GGT elevations due to treatment with bardoxolone methyl either remained at baseline levels or decreased. The ALT, AST, and GGT elevations were generally self-limiting in patients who continued treatment with study drug.

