#### **7.6.4. Week 12 (End of Treatment) Visit**

Week 12 is the final visit in the Treatment Period, and it marks the transition to the OT Period. Careful attention should be paid to ensure the visit is scheduled between Day 81 and Day 84, as outlined in [Table 4](#).

**Patients should be instructed to refrain from taking IP on the day of the Week 12 visit. The last dose of study drug should be the day prior to the Week 12 visit.**

If a patient permanently discontinues study drug early, please refer to Section [8.3](#).

Assessments to be completed at the Week 12/EOT Visit include the following:

- Review and record concomitant medications
- Review and record AEs
- Perform vital sign assessments (sitting blood pressure, pulse, heart rate, temperature, and weight)
- Collect/review weight and IP diary
- Perform 12 lead ECG at rest
- Perform a targeted physical examination, if needed
- Perform urine pregnancy test, if applicable
- Collect and review study drug

- Perform a buccal swab (cheek swab) for genetic testing (if not already collected)
- Collect blood and urine for clinical laboratory tests:
  - Clinical chemistry, including eGFR
  - BNP and NT-proBNP
  - Hemoglobin A1c
  - Hematology
  - Urinalysis and microscopy
  - Urine for UACR - first morning void specimen
  - Liver and Kidney Injury Biomarkers
  - C-Reactive Protein
  - PT/INR
- Collect blood for PK

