## **5.5. Derived and Transformed Data**

### **5.5.1. Study Day**

Study day is the day relative to the date of randomization. Day 1 is defined as the date of randomization. Assessments that occur after randomization but before the first dose of study drug are considered to occur on study Day 1.

Assessments without timestamp collected on the same date as the first date of study drug administration are considered to occur before the first dose of study drug administration.

For visits (or events) after randomization, day is calculated as:

- Study day = visit (or event) date - date of randomization + 1

For visits (or events) before randomization, day is calculated as:

- Study day = visit (or event) date - date of randomization

The quantity ‘days since first dose’ is defined as:

- days since first dose = visit (or event) date – date of first dose + 1

The quantity ‘days since last dose’ is defined as:

- days since last dose = visit (or event) date - date of last dose

For summaries that present distribution of time expressed in weeks and months, weeks are defined as days divided by seven and months as days divided by 30.4.

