### 9.1. Adverse Event Preferred Term and Body/Organ System Summary Tables

Treatment-emergent adverse events (TEAEs) are summarized by treatment as defined by the safety analysis set.

Treatment-emergent adverse events (TEAEs) are events that either:

- Have a date of onset on or after the date of first dose and not more than 30 days after the date of the last dose of study drug, or
- Have no recorded date of onset with a stop date after the first dose of study drug, or
- Have no recorded date of onset or stop date.

General considerations for TEAE summaries are:

- Multiple events by preferred term (PT) and system organ class (SOC) are counted once only per patient for summaries of TEAE incidence.
- For summaries of TEAE incidence by severity, only the most severe event is counted per patient.
- For summaries of TEAE incidence by relationship, only the most related event is counted per patient.
- A TEAE with a missing resolution date or incomplete date that is not identified as continuing is assumed to be continuing.
- For summaries of the number of TEAE events, all TEAEs are counted.
- Withdrawal TEAEs include the subset of TEAEs that started one to 30 days after the last dose of study drug.

Off-treatment AEs are events with a start date more than 30 days after last dose and not considered treatment emergent. Off-treatment AEs will be summarized separately.

AEs are coded using MedDRA (Medical Dictionary for Regulatory Activities) version 21.1. In MedDRA, each verbatim term is mapped to a preferred term and high level term (HLT), which is then mapped to a system organ class (SOC).

The investigator grades the severity of the AEs as mild, moderate, or severe as defined in the study protocol. The investigator grades association or relatedness to the study medication according to criteria specified in Section 11.4 of the protocol.

As defined in the protocol, a serious adverse event (SAE) is an adverse event (occurring at any dose and regardless of causality) that:

- Results in death;
- Is life-threatening;
- Requires inpatient hospitalization or prolongation of existing hospitalization;
- Results in persistent or significant incapacity or substantial disruption of the ability to conduct normal life functions;
- Is a congenital anomaly or birth defect in an offspring of a patient taking study drug;
- Is an important medical event.

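### The SAP's adverse-event timing displays do not divide the 12-week treatment period, so no table gives AE incidence by arm and onset interval on drug

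*SAP*

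**What the plan says.** Two displays in SAP 9.1.2 (Summaries of Adverse Events) concern timing. One is general: "TEAEs and OTAEs are summarized by treatment based on year of AE onset and overall". The other is a table of "TEAEs by time to onset" with a single cut at 12 weeks.

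SAP 9.1 adds two categories defined from the last dose. The first is a withdrawal subset: "Withdrawal TEAEs include the subset of TEAEs that started one to 30 days after the last dose of study drug". The second is off-treatment AEs, which start more than 30 days after the last dose and are summarized separately.

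The protocol describes when several known effects occur:
- Fluid overload and heart failure (5.1.2.1): in the earlier Phase 3 trial the excess risk "appeared to be limited to up to four weeks after initiation of treatment".
- Aminotransferases (5.1.2.2): "The elevations begin immediately after initiation of treatment or an increase in dose; they peak approximately two to four weeks later".
- Muscle spasms (5.1.2.3): mostly in the first two months.
- Nausea (9.1.8): linked to higher doses.

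Under Protocol 7.4.1 the dose steps up at Weeks 2 and 4, and at Week 6 for patients with baseline UACR above 300 mg/g.

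**The concern.** Safety and tolerability is one of the two primary objectives (Protocol 6.1.1). A timing table serves that objective if it separates periods in which the expected risk differs. Here the expected differences lie inside the 12 weeks of dosing, around initiation and the dose steps, while the single cut lies at the end of dosing.

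An excess of events in the first weeks would be added to the background events of the remaining weeks and reported as one count per arm. The AE tables would then not show a reader whether events clustered early, followed the titration, or were spread evenly.

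**Working it through.** The plan attaches no figure to AE timing, so the check is calendar arithmetic.

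**Inputs**
- SAP 5.5.1: "weeks are defined as days divided by seven".
- Protocol 7.6.4: "Careful attention should be paid to ensure the visit is scheduled between Day 81 and Day 84"; and "The last dose of study drug should be the day prior to the Week 12 visit".
- SAP 9.1: the TEAE window runs from first dose to 30 days after last dose.
- Protocol 7.1: end of study is 17 weeks after randomization.
- First dose is taken as Day 1, as the protocol schedules it.

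**1. Where dosing falls relative to the cut.** 12 weeks = 12 × 7 = 84 days. The last dose is on Day 81 − 1 = 80 to Day 84 − 1 = 83, that is 80/7 = 11.43 to 83/7 = 11.86 weeks. All scheduled dosing days are at or before 12 weeks.

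**2. What the later cell can hold.** For a patient treated on schedule, the TEAE window closes on Day 80 + 30 = 110 to Day 83 + 30 = 113 (15.7 to 16.1 weeks). Onset after Day 84 is therefore always post-dose.

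**3. Whether the later cell equals the withdrawal subset.** It does not. After a last dose on Day 83, an event on Day 84 is a withdrawal TEAE, yet 84/7 = 12.0 puts it in the earlier cell. Protocol 8.3.1 gives the example of a patient stopping at Week 5. That patient's TEAE window closes near Day 35 + 30 = 65, so all of the withdrawal TEAEs fall in the earlier cell. The two overlap but count from different origins.

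**4. The by-year grouping.** If year means study year, 17 weeks gives one level. If it means calendar year, it sorts events by enrolment date (first patient estimated for December 2020) and not by time since first dose.

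**5. What finer intervals would separate.** Days 1–28, 29–56 and 57 to the last dose contain 28, 28 and 24 to 27 dosing days, totalling 80 to 83. The first four weeks are 28/83 = 34% of the longest scheduled course.

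**6. Size of the dilution (illustration; hazard ratios and placebo risks are assumed, not in the documents).** Suppose the hazard ratio is h on Days 1–28 and 1 on the remaining 55 days. The average over 83 days is (28h + 55)/83:
- h = 2: 111/83 = 1.34
- h = 3: 139/83 = 1.67
- h = 5: 195/83 = 2.35

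With h = 3, 35 patients per arm and a constant placebo hazard giving 10% risk over 83 days, expected patients with an event (active versus placebo) are 3.54 versus 1.22 in the first four weeks (risk ratio 2.90). Over the whole period they are 5.66 versus 3.50 (1.62). With 5% placebo risk the ratios are 2.95 and 1.65.

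**The case against.** The strongest reply is that timing is reported elsewhere, and much of this stands.
- SAP 9.6.1 gives clinic weight and the proportion with a gain of at least five pounds by time point.
- SAP 9.5 summarizes laboratory results by time point and treatment, and 9.5.1 adds plots of BNP, ALT and AST.
- The analysis visits (Weeks 1, 2, 4, 6, 8 and 12) are finer than four-week intervals.
- SAP 9.1.2 lists all AEs, serious AEs and AEs leading to discontinuation or de-escalation. SAP 9.2 tabulates exposure by dose and visit.

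A reader might infer from the AE tables that the plan hides a four-week fluid-overload signal. The documents do not support that, because the weight and BNP outputs would show its time course. Nor do they support a liver-signal version. Protocol 9.1.2 expects nearly all aminotransferase elevations to be asymptomatic, and 11.6 makes laboratory changes AEs only when clinically significant, so the laboratory tables are the right instrument.

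A reader might also infer that the protocol predicts early fluid overload in this trial. The four-week finding comes from an earlier trial in Stage 4 CKD with type 2 diabetes. Protocol 5.1.2.1 says the risk had not been seen in six previous CKD studies. Protocol 8.2 and 9.1.1 exclude BNP above 200 pg/mL and clinically significant cardiac disease, including recent heart-failure hospitalization.

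Finally, for completers the 12-week cut approximates on- versus off-treatment, a sensible aim in a trial with a planned washout. The withdrawal and off-treatment categories already serve that aim from the correct origin.

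What the reply does not supply is AE incidence by arm and onset interval. Listings do not tabulate it. Muscle spasm and nausea have no visit-based measure to stand in for it. Daily home weights are not entered in the eCRF (Protocol 9.10.8), so the weight summaries rest on clinic values.

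**Conclusion.** The point holds in a limited form. Neither AE timing display divides on-treatment time, and the by-year grouping carries no information about time on drug. What is missing is a table of AE incidence by arm within the treatment period.

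This rests on dosing as scheduled. A late Week 12 visit could move a few dosing days past Day 84 without making the split informative. The dilution figures depend on assumed rates and show only the direction and rough scale.

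This is a weakness in descriptive reporting on a primary safety objective. No formal safety test is planned (SAP 9), no error rate, power or sample size changes, and no data are lost, since the table can be built from collected dates. It is worth correcting because the present split answers almost nothing and the replacement is cheap.

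**What to change.** In SAP 9.1.2:
- Delete the by-year grouping. The treatment-year grouping of concomitant medications in SAP 9.3 is uninformative for the same reason.
- Replace the 12-week cut with on-treatment onset from first dose in ≤4, >4 to ≤8 and >8 to ≤12 weeks. Count an event as on treatment if it starts on or before the date of last dose.
- Add a separate post-treatment row counted from last dose, matching the withdrawal definition in SAP 9.1.
- Give the number of patients at risk in each interval by arm.
- Show fluid-retention/heart-failure and muscle-spasm terms in these intervals. Leave aminotransferases to the laboratory outputs.
- State that the table is descriptive.

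The 4- and 8-week cuts follow time points in the protocol's safety background and monitoring, but they do not isolate each titration step. A display by dose level at onset, with placebo shown at its matched titration level, is optional. It must be labelled as confounded with time on study, because dose rises with time by design.

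The cost is a change of SAP wording and the reprogramming of one table. Onset dates are collected under Protocol 11.6. The only drawback is sparse cells with about 35 patients per arm.

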#### **6.1.1. Primary Objectives**

- To assess the change from baseline in estimated glomerular filtration rate (eGFR) at Week 12.
- To assess the safety and tolerability of bardoxolone methyl.

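### The planned adverse event tables cannot give the patients per arm with any fluid overload or heart failure event, or show whether onset falls in the first four weeks

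*SAP*

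**What the plan says.** **Adverse event tables.** SAP 9.1.2 lists nine tables of treatment-emergent events (TEAEs), introduced by "Summary tables (number and percentage of patients and events) of TEAEs (by SOC and PT) are provided by treatment as follows". They cover all events, related, by severity, serious, non-serious, related serious, leading to permanent discontinuation, by onset time, and a table headed "TEAEs exhibited in" more than 5% of patients. SAP 9.1 gives the counting rule: "Multiple events by preferred term (PT) and system organ class (SOC) are counted once only per patient for summaries of TEAE incidence". SAP section 9 defines no special-interest category, standardized query or term list.

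**Timing.** One table is "TEAEs by time to onset", cut at 12 weeks. SAP 9.1.2 also says "TEAEs and OTAEs are summarized by treatment based on year of AE onset and overall". SAP 9.1 sets apart events after dosing: "Withdrawal TEAEs include the subset of TEAEs that started one to 30 days after the last dose of study drug". None of these divides the 12 weeks of dosing.

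**The risk.** One of the two primary objectives is "To assess the safety and tolerability of bardoxolone methyl" (Protocol 6.1.1). Protocol 5.1.2.1 reports that "bardoxolone methyl treatment was found to be associated with an increased risk for fluid overload and heart failure hospitalizations in the BEACON trial", and adds that the excess appeared confined to at most four weeks from the start of treatment. Protocol 9.1.1 responds with exclusions, weight and BNP triggers, and an immediate drug stop when clinically important fluid retention is suspected.

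**What is already covered.** SAP 9.6.1 counts patients with a clinic weight gain of 2.3 kg or more by time point. SAP 9.5 and 9.5.1 summarize laboratory data by visit and arm and plot BNP. SAP 9.5.2 counts patients with BNP above 200 pg/mL or NT-proBNP above 1000 pg/mL at any time. Patients off the planned dose are listed with reasons (SAP 9.2), and interrupted patients form a subgroup (SAP 7.3).

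**The concern.** The protocol treats fluid overload as a risk that needs its own stopping rule. A reader of the safety results will want two facts: how many patients per arm had any such event, and whether the events came early. The planned adverse event tables supply neither.

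A preferred-term row counts patients for one term. A system-organ-class row counts patients once, but the class is not a fluid overload or heart failure group. Protocol 11.6 asks for one diagnosis per event, and for signs or symptoms where the diagnosis is unknown. The same clinical problem can therefore sit under different terms in different patients.

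Without a list fixed in advance, the group count has to be rebuilt from listings after unblinding, with the terms chosen while the results are in view. What is at stake is how clearly one named safety risk is reported. The primary efficacy analysis is not touched.

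**Working it through.** The plan gives no expected rate for these events and no figure of its own to reproduce. The check is whether the planned tables determine the two quantities. All event counts below are assumed.

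**Inputs.** 35 patients per arm, 70 in total (Protocol 12.1). Counting rule from SAP 9.1. Table list and 5% cut from SAP 9.1.2. Dosing for 12 weeks = 84 days, with 20 mg starting at Week 4 on schedule (Protocol 7.4.1). Study length 17 weeks.

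**1. Do term rows fix the group count?** For rows with r₁, r₂, … patients, the number of distinct patients lies between max(rᵢ) and min(35, Σrᵢ).
- Three rows of 2: from 2 to 6 patients, 2/35 = 5.7% to 6/35 = 17.1%.
- Four rows of 1: from 1 to 4 patients, 1/35 = 2.9% to 4/35 = 11.4%.

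The rows do not fix the count. The single-diagnosis rule in Protocol 11.6 limits overlap within a patient, so the low ends are less likely than the high ends.

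**2. What happens when terms scatter?** Suppose five drug-arm patients have five different fluid-related terms and nobody else has those terms. The exact (Clopper-Pearson) limits for x of n are the 2.5% quantile of Beta(x, n−x+1) and the 97.5% quantile of Beta(x+1, n−x).
- As a group: 5/35 = 14.3% (4.8–30.3%).
- As planned: five rows of 1/35 = 2.9% (each 0.1–14.9%).

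The SAP does not say whether the 5% cut applies per arm or overall. Per arm, 1/35 = 2.9% fails and 2/35 = 5.7% passes. Overall, 3/70 = 4.3% fails and 4/70 = 5.7% passes. None of the five term rows reaches that table on either reading. All five still appear in the all-TEAE table. A class row would show the total only if all five terms, and no others, fell in one class.

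**3. Can onset in the first four weeks be seen?**
- Four-week window: 28/84 = 33% of the dosing period.
- Remainder: 56/84 = 67%.
- Study length: 17 × 7 = 119 days, or 119/365 = 33% of a year.

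The 12-week cut falls at the end of planned dosing, so the early window shares one cell with the other two thirds. A split by year cannot usefully divide it.

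**4. Are fluid-related drug stops counted by arm?** Permanent discontinuations are tabulated by term and arm. Temporary stops appear only in the off-dose listing and the interruption subgroup. By contrast, SAP 11.1 does tabulate COVID-19 interruptions by arm.

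**5. Does the BNP count match the protocol's trigger?** Protocol 9.1.1 uses more than 100 pg/mL and at least double Day 1; SAP 9.5.2 uses more than 200 pg/mL. A rise from 40 to 150 pg/mL gives 150 > 100 and 150/40 = 3.75, so it meets the trigger, but 150 < 200, so it is not counted. SAP 5.4.5 averages all pre-dose laboratory values, and BNP is drawn at both Screen A and Day 1. The SAP baseline is therefore not the trigger's reference value.

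**The case against.** The case for leaving the plan alone is substantial. Safety is descriptive, with no formal testing, in about 70 patients, and no decision in either document depends on a grouped count. Every TEAE is tabulated by term and arm, and so are serious events and permanent discontinuations; all events are listed. Fluid retention is followed over time by arm through clinic weight and BNP. Protocol 5.1.2.1 adds that the excess risk had not been seen in six earlier CKD studies, and this trial excludes patients with raised BNP or significant cardiac disease. Section 5.1.2 describes six risks without ranking them. The five-term example is contrived, and finer tables at 35 per arm will hold mostly zeros and ones.

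Most of this stands, and it sets the size of the point. It does not supply the missing count. Weight and BNP are signals, not clinical events. The weight table uses clinic weights only, because daily home weights are not entered in the eCRF (Protocol 9.10.8). Eligibility from eGFR 20 also overlaps the 15 to 29 range enrolled in BEACON.

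A reader might infer that onset periods would show the effect of each dose. The documents do not support that. Escalation may be slowed (Protocol 9.1.2) or reversed (Protocol 7.4.2), and patients with UACR of 300 mg/g or less never receive 30 mg (Protocol 7.4.1). Calendar periods measure time since first dose only.

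**Conclusion.** The point holds as a gap in pre-specified tabulation. The planned adverse event tables do not give patients per arm with any fluid overload or heart failure TEAE, and they cannot separate the first four weeks from the rest of dosing. The absence is read directly from SAP section 9, and no redaction is visible in 9.1.2. The size is illustrative only: the percentages rest on assumed counts and 35 patients per arm.

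A reader might go further and conclude that events would be hidden, that fluid status is not monitored, or that the safety comparison is biased. None of these follows, given the full listings, the serious-event table and the weight and BNP summaries by visit. Nor is the 200 pg/mL BNP count an error. The protocol's trigger prompts a telephone contact, so it is a monitoring signal and not an event definition. This is a cheap improvement to descriptive safety reporting.

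**What to change.** Before unblinding, amend SAP 9.1.2 as follows.

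- Fix one preferred-term list for fluid overload/heart failure. Optionally give a narrow version (for example fluid overload, heart failure, pulmonary edema) and a broad one (adding for example edema, dyspnea, weight increased, BNP increased).
- Report by arm the number and percentage of patients with at least one such TEAE, each counted once, with an exact 95% CI. Show serious events separately.
- For this group, replace the 12-week split with Weeks 0–4, >4–12 and after last dose, labelled as time since first dose and not as dose level.
- Add one row by arm for patients with a temporary or permanent drug stop linked to such an event.
- Optionally, in SAP 9.5.2, count patients with post-baseline BNP above 100 pg/mL and at least double Day 1. Label it the protocol's monitoring trigger, and use the Day 1 value instead of the averaged baseline.

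The cost is one term list and a few rows from data already collected (event terms, dates and action taken under Protocol 11.6; stop reasons under 8.3.1). The terms must be chosen blind. Stops must be linked to adverse event records, because reasons such as adverse event are coarse. Cells will be sparse at about 35 per arm. If the data are already unblinded, the table is still worth producing, labelled post hoc.
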